14. CLINICAL OUTCOME ASSESSMENTS

14.1. Investigator Global Assessment (IGA)

The IGA will be performed at all study visits.

If a patient is assessed as “clear” (0) or “almost clear” (1), the patient will not be dispensed the study product. If a patient is assessed as “mild”, “moderate” or “severe” (2, 3 or 4, respectively), study product will be dispensed and the patient will use the study product daily according to patient instructions.

In the event a subject is not dispensed IP at a given visit due to an IGA of "clear" or "almost clear," and the subject's rosacea condition worsens, an unscheduled visit can be performed for assessing the subject and dispensing IP, if appropriate.

The IGA scale provided in [Table 1](#) will be used to describe the severity grade and subsequent score:

Table 1: Investigator Global Assessment (IGA) Scale

Grade	Description
0 – Clear	Skin clear of inflammatory papules or pustules
1 – Almost Clear	Very few small papules or pustules and very mild dull erythema is present
2 – Mild	Few small papules or pustules and mild dull or light pink erythema is present
3 – Moderate	Several to many small or larger papules or pustules and moderate light to bright red erythema is present
4 – Severe	Numerous small and/or larger papules or pustules and severe erythema that is bright red to deep red is present

14.2. Inflammatory Lesion Counts

Inflammatory lesions (papules and pustules) counts will be performed at Screening and Baseline, for new patients only, and they must have at least 15 and not more than 70 inflammatory lesions (papules, pustules) on the face.

Papules and pustules are defined as follows:

- **Papule** – A solid, elevated inflammatory lesion equal to or less than 5 mm in diameter
- **Pustule** – An elevated inflammatory lesion equal to or less than 5 mm in diameter, contains pus (yellow-white exudate)

Nodules will not be included in the inflammatory lesion count and are defined as:

- **Nodule/Cyst** – Palpable solid inflammatory lesion, greater than 5 mm in diameter, has depth, not necessarily elevated

14.3. Erythema Severity Assessments

Erythema is defined as redness of the skin. It will be scored on a scale of 0 (none) to 3 (severe) at Baseline, and at all the study visits except the screening visit. The Rosacea Erythema Assessment Scale is provided in [Table 2](#).

Table 2: Rosacea Erythema^a Assessment Scale

Grade	Description
0 – None	No visible erythema
1 – Mild	Slight erythema (dull or light pink), centro-facial
2 – Moderate	Definite erythema (light to bright red), either centro-facial or generalized to whole face
3 – Severe	Severe erythema (bright red to deep red), either centro-facial or generalized to whole face

^a Generalized erythema associated with rosacea

14.4. Telangiectasia Assessment

Facial telangiectasia will be evaluated on a scale of 0 to 3 at Baseline, and at all the study visits except the screening visit; the Telangiectasia is provided in [Table 3](#).

Table 3: Telangiectasia Assessment Scale

Grade	Description
0 – None	No Telangiectasia
1 – Mild	Only a few fine vessels discernible, involves approximately 10% or less of facial area
2 – Moderate	Multiple and more prominent fine vessels, involves approximately 10 – 30% of the facial area
3 – Severe	Numerous and prominent fine and/or courser vessels, involves more than 30% of the facial area

14.5. Rosacea Quality of Life (RosaQoL)

RosaQoL questionnaire will be taken at Baseline, Visits 5, 8, 11, 14 and at the End of Study Visit. There is a symptom subscale with seven questions (items 2, 6, 9, 16, 17, 18 and 19 in Appendix 2), a functional subscale with 3 questions (items 13, 15 and 21 in Appendix 2) and an emotion subscale with 11 questions (items 1, 3, 4, 5, 7, 8, 10, 11, 12, 14 and 20 in Appendix 2) to be administered in the study. The questionnaire will be administered to all patients during the designated study visits with the appropriate instructions from the Study Staff. The questionnaire should be completed:

- Only by the patient without amendment or interpretation of the patient's response by a clinician or anyone else.
- Prior to any other assessments or procedures.

In the event the patient skips any questionnaire items; the Study Staff will ask the patient to complete the form. The RosaQoL questionnaire data will be entered into the EDC system by the Study Staff, and a copy will be placed with the patient source documents at the site according to the ICH-GCP guideline (4.9.5).

All items should be scored for the following answers:

- Never: 1

- Rarely: 2
- Sometimes: 3
- Often: 4
- All the time:5

The Site Staff and anyone else provided with a copy of the RosaQoL instrument for the purpose of the study will be instructed that the RosaQoL instrument is protected by Common Law copyright. No part of this may be reproduced or transmitted in any form or by any means, now known or to be invented or adapted, for purpose of financial gain or profit.

An overall total score will be calculated; this score will be the unweighted mean of all RosaQoL questions. In addition to the total score, each subscale (symptom, functional and emotion) will also have a score calculated; these scores will be the unweighted mean of the group of questions that comprise the subscale. Further details on the handling of missing responses and calculation of the subscale scores will be detailed in the Statistical Analysis Plan (SAP).

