8.8.2.1 RosaQoL

The mean change in RosaQoL subscale scores from Baseline to Weeks 12, 24, 36, 48 and 52 will be summarized using descriptive statistics.

The subscores for the RosaQoL are computed as follows:

Total Score: the unweighted mean of all RosaQoL questions

Symptom subscale score: the unweighted mean of the following symptom questions

My rosacea burns or stings (item #2)

My rosacea is irritated (item #6)

My rosacea makes my skin sensitive (item #9)

My skin feels bumpy (uneven, not smooth, irregular) (item #16)

My skin flushes (item #17)

My skin gets irritated easily (cosmetics, aftershaves, cleansers) (item #18)

My eyes bother me (feels dry or gritty) (item #19)

Functional subscale score: the unweighted mean of the following functional questions

I try to cover up my rosacea (with make-up) (item #13)

I avoid certain foods or drinks because of my rosacea (item #15)

I avoid certain environments (heat, humidity, cold) because of my rosacea (item #21)

Emotion subscale score: the unweighted mean of the following emotion questions

- I worry that my rosacea may be serious (item #1)
- I worry about getting scars from my rosacea (item #3)
- I worry that my rosacea may get worse (item #4)
- I worry about side effects from rosacea medications (item #5)
- I am embarrassed by my rosacea (item #7)
- I am frustrated by my rosacea (item #8)
- I am annoyed by my rosacea (item #10)
- I am bothered by the appearance of my skin (redness, blotchiness) (item #11)
- My rosacea makes me feel self-conscious (item #12)
- I am bothered by persistence/reoccurrence of my rosacea (item #14)
- I think about my rosacea (item #20)

Each individual item should be scored as follows: 1=Never, 2=Rarely, 3=Sometimes, 4=Often, and 5=All the time. Missing data values will not be used. If a subscale has items with missing results, the subscore and the total will not be calculated.

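### One blank RosaQoL item voids its subscale and the 21-item total; a minimum-answered-items rule would keep most of these scores at little cost

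*Protocol*

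**What the plan says.** Protocol 14.5 sets out 21 items scored 1 to 5, grouped as symptom (7 items), functional (3) and emotion (11). Each subscale score is the plain mean of its items. For the total: "An overall total score will be calculated; this score will be the unweighted mean of all RosaQoL questions". For blanks at the visit: "In the event the patient skips any questionnaire items; the Study Staff will ask the patient to complete the form". For blanks that remain, the Protocol sets no rule and points elsewhere: "Further details on the handling of missing responses and calculation of the subscale scores will be detailed in the Statistical Analysis Plan (SAP".

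SAP 8.8.2.1 supplies the rule: "If a subscale has items with missing results, the subscore and the total will not be calculated". It also names the analysis: "The mean change in RosaQoL subscale scores from Baseline to Weeks 12, 24, 36, 48 and 52 will be summarized using descriptive statistics". The table shells go further than that sentence. Tables 14.2.2.1 and 14.2.2.2 give change rows for the total as well as for each subscale, each with its own n.

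SAP 8.1.2 takes baseline from the parent studies (54-01/54-02). SAP 8.1.3 also takes the Week 12 value from there for patients who received S5G4T-1 in those studies. SAP 8.1.5 imputes only certain dates and otherwise summarizes observed cases. Protocol 18.4.4 labels RosaQoL change exploratory.

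**The concern.** The rule is all or nothing. A patient who answers 20 of 21 items has given nearly everything needed for a mean on a 1-to-5 scale, yet contributes no total at that visit and no score for the affected subscale. The other two subscales survive. A change score needs two complete forms, so the total's change row depends on 42 answers without one blank. Because baseline is a single form reused for every comparison, a blank there costs the patient's total change score at all later visits, and a prompt given during 54-07 cannot reach back to it.

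At stake is the precision of the RosaQoL rows, most of all those for the total. The n will also differ between the total and the subscales, and patients who answer every item at both visits may not be typical of the rest.

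**Working it through.** **Inputs from the documents.** Item counts (Protocol 14.5): 7 + 3 + 11 = 21. The three item lists cover items 1 to 21 once each, so any one blank falls in exactly one subscale and always voids the total. A change in the total uses 2 × 21 = 42 answers.

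**Inputs not in the documents.** The per-item skip rate *p* left after the staff prompt, and how far skips cluster within patients. Both are assumed and varied below. The plan gives no expected completeness, so there is no planned figure to reproduce.

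**Loss under the SAP rule, independent skips.** P(score lost) = 1 − (1 − p)^k, with k = 21 for the total and k = 42 for its change.

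| p | total lost | change in total lost |
|---|---|---|
| 0.1% | 2.1% | 4.1% |
| 0.25% | 5.1% | 10.0% |
| 0.5% | 10.0% | 19.0% |
| 1% | 19.0% | 34.4% |

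The 0.1% row is also what results if the prompt recovers 90% of skips that started at 1%.

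**Subscales at p = 1%.** Single visit: functional 1 − 0.99^3 = 3.0%, symptom 1 − 0.99^7 = 6.8%, emotion 1 − 0.99^11 = 10.5%. Change (twice the items): 1 − 0.99^6 = 5.9%, 1 − 0.99^14 = 13.1%, 1 − 0.99^22 = 19.8%.

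**Clustered skips.** With a beta-binomial model of mean p and intraclass correlation ρ, set a = p(1 − ρ)/ρ and b = (1 − p)(1 − ρ)/ρ. The chance of no blank in k answers is the product of (b + i)/(a + b + i) over i = 0 to k − 1. At p = 1%, using the same ρ within and between visits:

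- ρ = 0.1: total lost 10.6%, change lost 14.9%.
- ρ = 0.3: total lost 5.7%, change lost 7.1%.

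Whatever the dependence, the loss at p = 1% lies between p and kp: 1% to 21% for the total, 1% to 42% for its change.

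**Precision.** Keeping a share s of the change scores inflates the standard error by 1/√s. A 19.0% loss gives 1/√0.810 = 1.11; a 34.4% loss gives 1/√0.656 = 1.23.

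**Loss under an at-least-half rule, p = 1%, independent skips.** Functional (2 or more of 3 blank): 3 × 0.01² × 0.99 + 0.01³ = 0.0298%. Symptom (4 or more of 7 blank) is 3 × 10⁻⁷ and emotion (6 or more of 11 blank) is 4 × 10⁻¹⁰. If the total is scored only when all three subscales can be, its loss is essentially the functional figure, about 0.03%. These figures rest on independence too; no such rule rescues a form that is mostly or wholly blank.

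**How far a dropped item can move a score.** With one blank of 21, the mean of the other 20 differs from the full mean by (missing answer − mean of the other 20)/21. That is 1/21 = 0.05 for a one-point difference and at most 4/21 = 0.19. With one blank of 3 on the functional subscale the divisor is 3, giving 0.33 per point.

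**Baseline.** SAP 8.1.2 uses the last non-missing assessment before first application in the parent study. If the baseline form has a blank, its total is not calculated, and the change score is lost at every later visit unless the parent study holds an earlier complete pre-dose form. The documents do not say whether it does.

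**The case against.** The rule is explicit, prespecified and programmable. It fits a total defined over all questions, and it fits the statements in Protocol 18.1 and SAP 8.1 that missing data are not imputed. Staff already prompt for skipped items at the visit. RosaQoL is exploratory in a study not designed to assess efficacy, no test is attached to it, and every row prints its own n, so any loss would be visible. The items differ in content: one concerns covering up with make-up, another dry or gritty eyes. A functional mean from two of three items therefore reflects a different mix, and a blank at only one visit makes the change compare different item sets.

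Much of this stands. The rule is not an error and contradicts nothing. A reader might infer three stronger things, none of which the documents establish:

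- That a large share of scores will be lost. This needs a skip rate and a dependence pattern that are not given; with a low residual rate or strong clustering, the loss is a few percent.
- That the retained patients are a biased selection. This is possible but not shown.
- That the mean of answered items estimates the same quantity as the full mean. This holds only if skipped items behave like answered ones.

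The no-imputation statements do not block the change. Averaging answered items is a scoring choice, and Protocol 14.5 leaves both missing responses and score calculation to the SAP. Nor does prompting settle the matter: staff may ask, but the answers must come from the patient alone, and the SAP itself provides for blanks that remain.

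**Conclusion.** The point holds as a low-cost improvement. The deletion rule is certain, and so is its reach: one blank voids the total and discards 20 given answers for it. For small independent skip rates, the loss is roughly 21 times the rate for the total and 42 times for its change. The amount lost in practice is unknown. A 10% loss of totals would need a residual skip rate of 0.50%, and a 10% loss of total change scores 0.25%, both under independence. Clustering at a 1% rate brings the loss down to about 6% to 11% of totals and 7% to 15% of change scores. The consequence is wider uncertainty, and possibly some selection, in descriptive quality-of-life rows. Adverse events, cutaneous safety and local tolerability are untouched.

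**What to change.** In SAP 8.8.2.1, replace the all-or-nothing sentence with these rules:

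- Score each subscale as the mean of its answered items when at least half are answered: symptom 4 of 7, functional 2 of 3, emotion 6 of 11.
- Score the total as the mean of all answered items when every subscale can be scored.
- Apply the same rule to parent-study item responses used in 54-07, where those are available.
- Keep the all-items-complete score as a sensitivity row, which matters most for the three-item functional subscale.
- Report the number of incomplete forms at each visit.

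The cost is a few lines of text and code, and the SAP's preface allows updates before database lock. The downsides should be stated in the SAP: slightly more measurement error when fewer items are averaged, possible bias if skipped items differ from answered ones, and 54-07 baselines that may not match those in the parent-study reports.

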15. SAFETY EVALUATIONS

Safety will be assessed by monitoring incidence of Cutaneous Safety Assessment, Local Tolerability Assessment and adverse events reporting at all visits.

15.1. Cutaneous Safety Assessments

A qualified designee will assess local application site cutaneous reactions by rating the dryness and scaling at Baseline, and at all the study visits except the screening visit. The evaluator will determine the score for each of these variables by direct evaluation. The definitions of grades provided in [Table 4](#) will be applied to these evaluations. The Cutaneous Safety Assessment of dryness and scaling will be made by the investigator at the time of the visit.

Table 4: Cutaneous Safety Assessment Scale

Grade	Description
Dryness	
0 – None	No dryness
1 – Mild	Slight but definite dryness
2 – Moderate	Moderate dryness
3 – Severe	Marked dryness and/or cracking
Scaling	
0 – None	No scaling
1 – Mild	Barely perceptible scaling
2 – Moderate	Obvious but not profuse scaling
3 – Severe	Heavy scale production and/or peeling

Application site reactions (dryness and scaling) are not to be recorded as adverse events unless they result in either:

- The temporary discontinuation of the study product.
- The discontinuation of the patient from the study.
- The use of a new concomitant medication in order to treat this event.

Any other application site reaction not listed above (such as pain) should be recorded as adverse events in the source document and eCRFs.

15.2. Local Tolerability Assessments

A qualified designee will assess local application site tolerability by rating the itching and burning/stinging at Baseline, and at all the study visits except the screening visit. The evaluator will determine the score for each of these variables by asking the patient to grade their experience over the **past 24 hours**. The definitions of grades provided in [Table 5](#) will be applied to these evaluations. The Local Tolerability Assessment evaluations of itching and burning/stinging will be made by the investigator at the time of the visit.

Table 5: Local Tolerability Assessment Scale

Grade	Description
Itching	
0 – None	No itching
1 – Mild	Slight itching, not really bothersome
2 – Moderate	Definite itching that is somewhat bothersome
3 – Severe	Intense itching that may interrupt daily activities and/or sleep
Burning/Stinging	
0 – None	No burning/stinging
1 – Mild	Slight burning/stinging sensation; not really bothersome
2 – Moderate	Definite warm, burning/stinging sensation that is somewhat bothersome
3 – Severe	Hot burning sensation that causes definite discomfort and may interrupt daily activities or sleep

Application site reactions (itching and burning/stinging) are not to be recorded as adverse events unless they result in either:

- The temporary discontinuation of the study product.
- The discontinuation of the patient from the study.
- The use of a new concomitant medication in order to treat this event.

Any other application site reaction not listed above (such as pain) should be recorded as adverse events in the source document and eCRFs.

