--	--

	
 13. Use of medicated cleansers on the face (e.g., benzoyl peroxide, salicylic acid, sulfur or triclosan) within 7 days of Baseline and throughout the study. 14. Patient consumes excessive alcohol, abuses drugs, or has a condition that could compromise the patient's ability to comply with study requirements and/or have drug or alcohol addiction requiring treatment in the past 12 months. 15. Use of topical astringents or abrasives (e.g., rubs, exfoliating cleansers and products containing salicylic acid and/or alcohol), topical preparations that contain spices or lime, medicated topical preparations (prescription and OTC products) within 7 days prior to Visit 2 (Baseline) and throughout the study. 16. Use of antipruritics (including antihistamines), spa or sauna treatments or chlorine exposure (swimming pool etc.) within 24 hours (1 day) of all study visits (Visit 2, Baseline, through End of Study). 17. Participation in any clinical study involving an investigational product, agent or device that might influence the intended effects or mask the side effects of study product, within 30 days prior to Visit 2 (Baseline) and throughout the study. 18. Previous enrollment in this study or current enrollment in this study at another participating site. 19. Employee (or employee's family member) of the research center or private practice, or patients who have a conflict of interest. 20. Patients living (e.g., siblings, spouses, relatives) in the same household cannot be enrolled in the study at the same time. 21. Use of tanning booths, sun lamps or excessive UV radiation (e.g., phototherapy, daily extended exposure or occupational exposure to the sun), sunbathing or excessive exposure to the sun 1 week (7 days) prior to Baseline and throughout the study. 22. Patients who in the opinion of the investigator, are unlikely to be able to follow the restrictions of the protocol and complete the study.
Safety Endpoints:	
 • Adverse events (AEs), including serious adverse events (SAEs) occurring at any time during the trial. • Investigator Cutaneous Safety Assessment and Local Tolerability Assessments score at any time during the trial.

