18.4. Safety Evaluation

Safety will be evaluated by tabulations of adverse events (AEs), Cutaneous Safety Assessments for dryness and scaling, Local Tolerability Assessment for itching and burning and assessments for erythema and telangiectasia will be presented with descriptive statistics at Baseline and at the scheduled study visits. Frequencies and percentages for each outcome category will be included in these statistics. Safety data will be presented for patients in the Safety Population with tabulations for the following periods 12 to 28 weeks, > 28 to 52 weeks and > 52 weeks to the end of the study, as well as an overall for all periods.

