8.9.2 Adverse Events

AEs from 54-01/02 will be included in the analysis for 54-07. All AEs that were reported as ongoing in 54-01/02 will be added into the CRF for 54-07, while AEs reported as recovered/resolved will be pulled forward programmatically into 54-07.

AEs occurring during the study will be recorded and classified on the basis of MedDRA terminology. Descriptions of AEs will include the date of onset, the date the AE ended, the severity of the AE, the relationship to study product, the action taken regarding study product usage, the action taken to treat the AE, and the outcome. All reported treatment-emergent AEs (TEAEs) will be summarized by the number of patients reporting AEs, system organ class, severity, seriousness, and relationship to study product. TEAEs are those AEs with an onset on or after the date of the first study product application. For AEs recorded in the 54-07 study if the AE is not indicated as prior to first application on the CRF then it will be considered a TEAE. AEs from 54-01/02 for subjects who received S5G4T-1 in 54-01 or 54-02 will be considered a TEAE if they were considered at TEAE in the 54-01/02 study. AEs (including ongoing) from 54-01/02 study for subjects who received vehicle in 54-01 or 54-02 will be considered pre-treatment.

AEs will be summarized by period (and total) and by severity. Each patient will be counted only once within a SOC or a Preferred Term by using the AEs with the highest severity within each category.

AEs will be summarized by period (and total) and by relationship to study product. Each patient will be counted only once within a system organ class or a preferred term by using the AEs with the greatest relationship within each category.

If relationship to study drug is reported as definitely, probably, or possible, then this is defined as related. If relationship to study drug is reported as unlikely or not related, then this is defined as unrelated.

TEAEs will be summarized in total as well as by the following periods based on time of onset in relation to date of first application of S5G4T-1, based on the definitions below. Start dates will be imputed as described in Section 8.1.5.2.

- 0-12 Weeks $0 \leq \text{onset day} \leq 85$
- >12-28 Weeks $86 \leq \text{onset day} \leq 197$
- >28-52 Weeks $198 \leq \text{onset day} \leq 365$
- >52 Weeks $\text{onset day} \geq 366$

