8.9.4 Other Observations Related to Safety

8.9.4.1 Cutaneous Safety Assessments

Descriptive statistics by visit will be provided for dryness and scaling.

Cutaneous Safety Assessments will be presented in a by-subject listing.

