8.9.4.2 Local Tolerability Assessments

Descriptive statistics by visit will be provided for itching and burning/stinging.

Local tolerability data will be presented in a by-subject listing.

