10. CHANGES IN THE PLANNED ANALYSES

The protocol was written in a way that subjects who did not participate in 54-01 or 54-02 could be enrolled into 54-07. When the SAP was created, 54-07 was fully enrolled, and no subject was enrolled who did not complete the 54-01 or 54-02 study. The SAP was written such that any text from the protocol that discusses the new subjects was excluded.

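### No planned table counts patients by their worst dryness, scaling, itching or burning/stinging grade: a cheap, low-priority addition to Table 14.3.1.1

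*Protocol*

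**What the plan says.** **Recording rule.** Protocol 15.1: "Application site reactions (dryness and scaling) are not to be recorded as adverse events unless they result in either" one of three consequences. These are a temporary stop of product, the patient leaving the study, or a new medication to treat the event. Protocol 15.2 repeats the rule for itching and burning/stinging: "Application site reactions (itching and burning/stinging) are not to be recorded as adverse events unless they result in either" the same three.

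**Endpoint.** The synopsis names "Investigator Cutaneous Safety Assessment and Local Tolerability Assessments score at any time during the trial". Protocol section 8 and SAP section 5 word the endpoint by visit instead. Protocol 11 and 15 speak of monitoring the incidence of these assessments.

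**Analysis in the protocol.** Section 18.4 opens by asking for these scores, with frequencies by category, at baseline and the scheduled visits. It ends by asking for safety data by period, the last one running "to the end of the study, as well as an overall for all periods".

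**Analysis in the SAP.** Section 8.9.4.1: "Descriptive statistics by visit will be provided for dryness and scaling". Section 8.9.4.2: "Descriptive statistics by visit will be provided for itching and burning/stinging". Both add a by-subject listing. Period and total summaries are specified for adverse events: "TEAEs will be summarized in total as well as by the following periods based on time of onset" (SAP 8.9.2).

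**Windowing.** SAP 8.1.3 leaves an ET or unscheduled score out of the analyses if it was taken before 54-07 Day 22, after Day 378, or in a window that already has a scheduled score. Listings keep all of them.

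**The concern.** Safety is the study's only objective, and these scores are one of its two stated safety endpoints. A patient with grade 3 itching who carries on untreated enters no adverse event table. That patient appears only as one count in one visit's cell, or only in the listing if the score fell outside the windowing rule.

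By-visit percentages give the share affected at each visit. They do not give the share of patients who were ever severely affected, which is the usual per-patient statement of severity and frequency. SAP section 4 describes Phase 2 in that per-patient form. The planned 54-07 tables would not support the same sentence.

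**Working it through.** The plan gives no figure for this point, so there is none to reproduce. The check compares the planned displays with the question and then bounds what by-visit shares can tell.

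1. **Planned displays.** The SAP table index and shells contain one table for these scores, 14.3.1.1. It shows grades 0–3 at baseline and at each analysis visit, with the same pages repeated for all four reactions. Post-baseline blocks: 4 reactions × 13 visits = 52. None is a worst-grade, ever-grade-3 or overall block. Maximum severity per patient appears only in the adverse event tables. Listing 16.2.7.1 holds the individual scores.

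2. **Visits per patient (SAP 8.1.3).** Patients on S5G4T-1 in the parent study have Weeks 4 to 52, so V = 13. Patients on vehicle have Weeks 4 to 40, so V = 10.

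3. **What a by-visit share implies.** Suppose a share p is at grade 3 at each of V visits, with full attendance. The share ever at grade 3 is at least p (the same patients each time) and at most V × p (different patients each time). If visits were independent it would be 1 − (1 − p)^V. The value of p is assumed; the documents give none.

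| p | V | minimum | independent | maximum |
|---|---|---|---|---|
| 0.5% | 13 | 0.5% | 6.3% | 6.5% |
| 1% | 13 | 1% | 12.2% | 13% |
| 2% | 13 | 2% | 23.1% | 26% |
| 1% | 10 | 1% | 9.6% | 10% |

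For the planned 700 patients, if all had 13 visits and p = 1%, the limits are 700 × 0.01 = 7 and 700 × 0.13 = 91 patients. If every grade 3 cell is zero, the range closes and only the scores left out of the table matter.

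4. **Which scores are left out.** Scheduled scores are kept whatever their day; a Week 4 visit can fall on Day 29 − 10 = 19. ET scores from Day 22 to Day 378 are kept when their window has no scheduled score. A reaction that caused withdrawal, a pause or new medication is an adverse event under 15.1 and 15.2, so it reaches the adverse event tables anyway. What remains is unscheduled scores without such a consequence and ET scores from patients leaving for other reasons. Day 22 counts from 54-07 baseline. For S5G4T-1-parent patients it falls about 15 weeks into exposure (12 weeks plus 22 days). For vehicle-parent patients dispensed product at baseline, the days before it are the first three weeks on product.

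5. **Evidence on rates (SAP section 4).** Phase 2 ran 12 weeks with 92 patients across all arms. None had severe dryness, scaling or pruritus after baseline. One patient in the 5% group had severe stinging and burning, reported as an adverse event. Zero of 92 has a one-sided 95% upper bound of 1 − 0.05^(1/92) = 3.2%. Zero of 700 would give 1 − 0.05^(1/700) = 0.43%.

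6. **Limit of any such count.** Itching and burning/stinging are graded over the past 24 hours, so scheduled visits cover 13/365 = 3.6% or 10/281 = 3.6% of days.

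**The case against.** The strongest case is that the SAP already does what the protocol asks. The first sentence of Protocol 18.4 names these scores and calls for descriptive statistics at the scheduled visits. Protocol section 8 and SAP section 5 are also visit-based, and the SAP takes precedence where the documents differ. This stands.

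A reader might infer an undeclared departure from the protocol. The end of 18.4 asks for an overall summary, and SAP section 10 lists only one change: "The SAP was written such that any text from the protocol that discusses the new subjects was excluded". The documents do not support that inference. The period sentence is general, Protocol 18.4.2 applies period and total to adverse events, and an overall summary need not be a worst grade per patient.

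A reader might also infer that severe reactions would go unseen or be lost. They would not. Grade 3 counts are shown at every visit, reactions with a consequence become adverse events, and Protocol 16.2 notes that severe events usually need treatment. Every score is listed, so the count could be programmed later from existing data.

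Phase 2 gives no sign of frequent severe reactions, though it covers only 12 weeks. The objection does not remove the basic point: no planned table gives the per-patient count, and some scores reach no table.

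**Conclusion.** The point holds as a reporting gap of low priority. By-visit tables meet the visit-based wording of the plan, but they do not answer how many patients ever had a severe score. The synopsis wording and the references to incidence make that a natural question.

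The effect is unquantified. The 1% to 13% range rests on an assumed constant rate and full attendance, and its top needs different patients at each visit; it should not be read as an estimate of impact. The number of scores dropped by SAP 8.1.3 is unknown and is limited to those without an adverse event consequence. No decision rule or patient protection depends on the result. Fixing the summary before database lock is still better than choosing it after the data are seen.

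**What to change.** Add to Table 14.3.1.1, with matching text in SAP 8.9.4.1 and 8.9.4.2, one block for each of the four reactions:

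- Number and percent of Safety Population patients by worst grade (0–3) after first S5G4T-1 application, each patient counted once.
- All collected scores used, including ET and unscheduled visits on any day, and parent-study scores for S5G4T-1-parent patients.
- Columns by parent-study treatment and overall, because the two groups have 13 and 10 analysis visits.
- Cross-tabulation by the last score before first S5G4T-1: the 54-01/02 baseline for S5G4T-1-parent patients and 54-07 Visit 2 for vehicle-parent patients. The SAP 8.1.2 baseline would be about 12 weeks too early for the vehicle group and would count reactions that arose on vehicle as new.
- Footnotes that itching and burning/stinging scores cover only the 24 hours before a visit, and that some scores come from periods off product (IGA 0 or 1).

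Matching grade 3 patients to treatment-emergent adverse events by preferred term is optional. The recording rule in Protocol 15.1 and 15.2 stays as it is.

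Cost: minor programming on data already collected, with no protocol change or new assessment, and possibly a less favourable count of severe reactions. It cannot recover itching or burning between visits.
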